##### 9.1.1.2 Timing of Assessment

Will be performed within six weeks prior to or on Visit 3. The investigators will attempt to schedule the mpMR as close to the date of the PET/CT so that the post-TRUS biopsy changes do not confound the differences between the two imaging modalities.

#### 9.1.2 $^{89}\text{Zr}$ -df-IAB2M PET/CT imaging

##### 9.1.2.1 Method of Assessment

PET/CT will be read twice by a nuclear medicine physician. For the first interpretation, the physician will be blinded from clinical history, biopsy results and conventional

imaging modalities. After the initial reading, the nuclear medicine physician will be provided with both the TRUS biopsy results and previously read scans for the repeat PET/CT reading. During each interpretation, the physician will record all abnormal, suspicious areas with higher uptake than adjacent or contralateral background. Each abnormal area will be recorded on a map of the prostate along with maximum standardized uptake value ( $SUV_{max}$ ) and mean standardized uptake value ( $SUV_{mean}$ ).

Subsequently, the accumulation of  $^{89}Zr$ -df-IAB2M will be compared to areas of known PCa foci on histopathology and mpMRI, as described in Section 13. After completion of the histopathology, the PET/CT findings will be compared to histopathology to perform a lesion by lesion analysis with histopathology serving as the reference gold standard. This analysis will primarily include tumors  $\geq 0.5 \text{ cm}^3$  on histopathology, with a secondary assessment of any lesions  $<0.5 \text{ cm}^3$ . Similarly, areas of increased uptake identified on IAB2M, which had been read as suspicious for cancer will be compared to histopathology to determine the underlying pathology (e.g., inflammation, benign prostatic hyperplasia).

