## 2.3 Rationale

### Zr-df-IAB2M for PCa imaging/diagnosis

An ad-hoc analysis of data from 18 subjects with metastatic PCa showed that the combination of conventional imaging (CT, bone scan, FDG PET) and Zr-df-IAB2M PET imaging identified a total of 168 lesions (152 bone lesions and 16 soft tissue lesions). Thirty-four of these 168 lesions (32 bone lesions and two soft tissues lesions) were identified by Zr-df-IAB2M PET but not by conventional imaging. A total of 13 biopsies in these 18 patients confirmed true-positive identification of lesions in 11 of 11 locations and true-negative identification in one of two locations using Zr-df-IAB2M compared with nine of 11 positive lesions and two of two negative lesions correctly identified by FDG PET. This improved sensitivity and specificity illustrates the potential of Zr-df-IAB2M PET to provide clinicians with actionable information that may improve the accuracy of diagnosis, staging of the disease, risk stratification, and treatment decision-making.

Further review of Zr-df-IAB2M PET/CT by an independent third-party core lab was undertaken to determine the ideal unlabeled protein dose(10, 20 and 50 mg) and timing of

optimal imaging for lesion detection. This un-blinded analysis revealed predominantly pelvic and lumbar spinal bone metastases and nodal metastases detection in the 18 subject cohort. Based on both estimated lesion detection rate, PET/CT activity and reader preference, the 48 hour imaging time point was determined to be the best time point for lesion detection and quantitation, while the time points from 24 hours through 96 hours demonstrated comparable qualitative and quantitative results to the 48 hour time point. Increasing unlabeled antibody affected the time course of detection of prostate metastases in all tissues examined, with the 10 mg cohort demonstrating the most sensitivity for lesion detection and quantitation. These results suggested that Zr-df-IAB2M can be an effective probe for the PCa marker PSMA and provide a robust imaging scan to better detect PCa tumor burden.

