#### 9.1.3 $^{68}Ga$ -PSMA-HBED-CC PET/CT imaging

Patient preparation should be according to the policies and procedures of the local imaging site (CIBC). The patient does not need to be fasting for either the infusion or the scans. The use of intravenous or oral contrast will not be permitted. Specifications for acquiring the  $^{68}Ga$ -PSMA-HBED-CC PET/CT scans will be provided in study specific documentation by the study chair or the co-investigators from the Division of Nuclear Medicine. PET/CT images are acquired between 1 and 3 hours after the  $^{68}Ga$ -PSMA-HBED-CC infusion. Image acquisition will be from vertex of skull to mid thighs. The subject will be scheduled for the injection and imaging between screening and prostatectomy depending on subjects' availability and compliance.

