- e Radiographic evaluations include a modified (3T multiparametric) MRI of the pelvis, if clinically indicated. Radiographic studies are to be performed within 6 weeks before, or on Visit 3/Day 2, provided the patient has not received a new intervening anti-cancer treatment.
- f Blood sample will be drawn via venipuncture for HAHA evaluation pre-infusion at Visit 3 and repeat samples will be taken at Visit 5 (week 6, +/- 1 week).
- g Ga-PSMA-HBED-CC administration followed by PET/CT scan 1 – 3 hours later must be done prior to Zr-df-IAB2M tracer administration on Visit 2 otherwise the Ga-PSMA-HBED-CC administration and PET/CT scan can be done anytime between screening and prostatectomy visit.

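### The blind for the first 89Zr-df-IAB2M read does not name the 68Ga-PSMA PET added in Amendment v3, and that scan has no reading rule of its own

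*Combined protocol and SAP*

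**What the plan says.** Section 9.1.2.1 states that the 89Zr "PET/CT will be read twice by a nuclear medicine physician". At the first reading "the physician will be blinded from clinical history, biopsy results and conventional" imaging. The second reading is open: "After the initial reading, the nuclear medicine physician will be provided with both the TRUS biopsy results and previously read scans". A focus is recorded when its uptake exceeds that of neighbouring or opposite-side tissue, which is a visual judgement.

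Section 9.1.3, on the 68Ga scan, covers preparation, acquisition ("PET/CT images are acquired between 1 and 3 hours after the" infusion) and scheduling ("The subject will be scheduled for the injection and imaging between screening and prostatectomy"). It names no reader, reading order, blinding or lock. Footnote g of the study calendar requires the 68Ga scan to come before the 89Zr "tracer administration on Visit 2 otherwise the" 68Ga scan may fall at any point from screening up to surgery.

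Section 12.1 defines the primary endpoint as the share of subjects with a dominant PSMA-positive lesion over 5 mm whose lesion was found on 89Zr imaging. It assumes 75% success in 20 patients and gives ±19.0% for the 95% interval. It does not say which of the two 89Zr readings supplies the endpoint. Secondary analyses compare each PET tracer with mpMRI by sector and test the added value of combining modalities. Section 9.1.4 blinds the pathologist to imaging.

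**The concern.** The plan evidently wants one 89Zr reading made without outside help. 68Ga-PSMA PET images the same antigen in the same gland, so it is a strong cue to where the 89Zr reader should look. A reader who knows the 68Ga focus is more likely to call faint 89Zr uptake there, and the success is credited to 89Zr.

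The same lack of separation, in either direction, would make the two tracers' sector results resemble each other when each is set against mpMRI. It would also blur any gain attributed to adding one modality to another. A 68Ga read made with knowledge of histology would distort the 68Ga accuracy figures as well.

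**Working it through.** **1. Is the 68Ga scan covered by the blind?** It is not named in Section 9.1.2.1, so it is covered only if it counts as conventional imaging.
- Section 2.3 uses the term for "conventional imaging (CT, bone scan, FDG PET"), but there it describes an earlier cohort of 18 metastatic patients.
- Section 2.4 contrasts PET with conventional methods.
- Exclusion 3.2.1 uses the term for this trial without listing what it includes.
- The 68Ga agent is investigational, under its own IND.

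The usage points away from inclusion, but there is no trial-specific definition. The list is therefore silent on the 68Ga scan; it does not exclude it expressly.

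**2. Can the 68Ga result exist before the first 89Zr read?** Yes. If the 68Ga scan is done at Visit 2 (Day 0), it must precede the 89Zr tracer, and the 89Zr scan follows at Visit 3 (Day 2 to 4 in the calendar). Otherwise it may come earlier, from screening onwards, or after the 89Zr scan. The date of the 89Zr reading is not stated.

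**3. Can the 89Zr reader know it?** Releasing earlier scans only after the first reading implies that they are withheld until then. The gap that remains is a physician who read the 68Ga scan personally. The study is single-centre (Section 12.1), and nothing requires a different reader. In the other direction, no text protects the 68Ga read from the 89Zr result or from histology.

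**4. The plan's precision figure.** Inputs from Section 12.1: n = 20, p = 0.75, two-sided 95%.
- Wald half-width = 1.96 × √(0.75 × 0.25 / 20) = 0.1898, or ±19.0 points. The stated figure reproduces.
- At 15/20, the Wilson interval is 53.1% to 88.8% and Clopper-Pearson is 50.9% to 91.3%.

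All of these describe sampling error only.

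**5. Illustrative bias.** Let c be the share of true 89Zr misses that a primed reader turns into hits, and e the share of patients in whom the exposure occurs. Neither is in the documents; both are assumptions. Taking exposure as unrelated to whether 89Zr misses the lesion, bias = (1 − 0.75) × c × e.

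| c | e = 1 | Patients of 20 (e = 1) | e = 0.5 |
|---|---|---|---|
| 0.10 | +2.5 points (77.5%) | 0.5 | +1.25 |
| 0.25 | +6.25 (81.25%) | 1.25 | +3.1 |
| 0.50 | +12.5 (87.5%) | 2.5 | +6.25 |

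One converted patient moves the proportion by 1/20 = 5 points at the end, and by 1/10 = 10 points at the interim look in Section 12.3.

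**The case against.** The strongest reply is that Section 9.1.2.1 already handles this. The scans released for the second reading are not limited to conventional modalities, so in its natural sense the sentence withholds a 68Ga scan that has already been read. The leak then needs a fact that the documents do not state: that the same physician read the 68Ga scan first. This stands as a partial safeguard, and it is why exposure is only possible. It does not cover a reader's own memory, and it says nothing about how the 68Ga scan is read.

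Two further points stand. The study is an exploratory pilot with hypothesis-generating estimates, no formal power calculation and a blinded pathologist. The mpMRI comparison is already uneven, because the radiologist has the TRUS biopsy results (Section 9.1.1.1). Both lower the severity. Neither supplies the missing rule.

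A reader might infer three stronger things that the documents do not support:
- *That Section 2.3 defines conventional imaging for this trial.* It describes another cohort. Taken as the definition, it would also put mpMRI outside the blind.
- *That the bias can exceed the ±19-point precision.* Suppose 68Ga shows 40%, 60% or 86% of 89Zr misses and half or all of those are converted. The gain is 0.25 × those products, from 5 to 21.5 points. Only one of the six combinations (0.25 × 0.86 × 1 = 21.5) passes 19. It needs full conversion, universal exposure and independent misses by two tracers that bind the same antigen. The 86% is the per-patient summary sensitivity in Section 2.2, from a review that the reference list titles as concerning advanced disease, not dominant lesions within the gland.
- *That blinding the first read by itself protects the primary endpoint.* It does so only if that read is the one used, and the plan does not say so.

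**Conclusion.** The point holds as a gap in the written rules, not as a demonstrated unblinding. Followed as written, the plan allows a first 89Zr read by someone who already knows the 68Ga result, and leaves the 68Ga read with no protection at all. Any resulting bias in the primary endpoint runs towards 89Zr success.

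Its size cannot be derived from the documents. About 2.5 to 12.5 points is an illustration. It rests on the plan's 75%, an assumed conversion of 10% to 50% of misses, and exposure in every patient; at half exposure it is about 1.25 to 6.25. The ±19.0% interval reproduces but does not account for bias of this kind. The effect on the primary endpoint further assumes that the first read is the endpoint read.

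This should be fixed. It does not invalidate an exploratory pilot, but a read made with the other result known cannot be cleanly redone by a reader who has seen that result.

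**What to change.** 1. In Section 9.1.2.1, add 68Ga-PSMA PET/CT to what is withheld at the first 89Zr read: images, reports and any prior read by the same physician.
2. In Section 9.1.3, give the 68Ga scan a matching first read, blinded to clinical history, biopsy, mpMRI, 89Zr PET and histology. Existing readers suffice. If one physician reads both tracers, use coded images and leave an interval between a patient's two reads.
3. Lock both first reads before the other tracer's result or histology is released to the reader. Time this so that the reads for the first 10 patients are complete for the interim analysis in Section 12.3.
4. In Section 12.1, state that the blinded first 89Zr read is used for the primary endpoint.

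The cost is amendment wording and scheduling of reads that are needed anyway. There is no extra scan, reader or patient, and n = 20 and ±19.0% are unchanged. The small downside is that some study reads may be delayed or batched.

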#### 9.1.2.2 Timing of Assessment

Infusion of  $^{89}Zr$ -df-IAB2M will occur during Visit 2. Imaging will be performed 2-3 days after the injection on Visit 3. Please refer to the Calendar of Events (Section 10).

#### 9.1.3 $^{68}Ga$ -PSMA-HBED-CC PET/CT imaging

Patient preparation should be according to the policies and procedures of the local imaging site (CIBC). The patient does not need to be fasting for either the infusion or the scans. The use of intravenous or oral contrast will not be permitted. Specifications for acquiring the  $^{68}Ga$ -PSMA-HBED-CC PET/CT scans will be provided in study specific documentation by the study chair or the co-investigators from the Division of Nuclear Medicine. PET/CT images are acquired between 1 and 3 hours after the  $^{68}Ga$ -PSMA-HBED-CC infusion. Image acquisition will be from vertex of skull to mid thighs. The subject will be scheduled for the injection and imaging between screening and prostatectomy depending on subjects' availability and compliance.

#### 9.1.4 Histopathology

##### 9.1.4.1 Method of Assessment

All patients will undergo radical prostatectomy and potential lymph node dissection. The prostate gland will be fixed in formalin for 12-24 hours at room temperature. After fixation, the gland will be processed according to standard institutional protocol, as follows:

- 1) Weigh the prostate gland with attached seminal vesicles and vasa deferentia
- 2) Measure the prostate, seminal vesicles, and vasa deferentia

3) Orient the gland. Note and describe any nodularities or asymmetry to the gland; tissue disruptions; defects; or surface irregularities; adherent tissues/organs, etc.

4) Ink the entire specimen—green on the right side and black on the left.

5) Amputate both seminal vesicles and vasa deferentia at their attachment to the prostate and submit the most proximal portion of each for histology (i.e., submit the portion of SV/VD nearest their juncture with the prostate).

6) Amputate the most distal (apical) 5-7 mm of the gland. Place the broad cut surface of this “cone” of tissue onto the table and section perpendicularly to the midline (into ~3 mm strips). Submit the strips on “edge” for margin (ink) evaluation. When submitting, if the strips are not too long, leave the left and right sides connected and submit the anterior and posterior halves separately (e.g., A2- anterior apex, A3-posterior apex). If the strips are too long to fit into a cassette, divide the strips into left and right halves. Maintain the separation of anterior and posterior halves and designate appropriately in the summary of sections (e.g., A2- left anterior apex, A3-right anterior apex, A4-left posterior apex, A5- right posterior apex).

7) Amputate the most proximal (basal) 5-7 mm of the gland, which should include the bladder neck margin, and process this “cone” of tissue in the same manner as the apex (Step 6).

8) Section the remaining prostate perpendicular to the urethra into 4 mm thick slices, starting at the apex and continuing towards the base until completely sectioned. Designate the slices/levels as A, B, C, etc., starting from the apex. Generally, an average 35 gram prostate should be sectioned into at least five levels (A to E).

Sections to submit for histology: Right and left seminal vesicle and vas deferens (1-2 cassettes total, depending on size); Bladder neck/base margin (2-4 cassettes, divided as above); Apical margin (2-4 cassettes, as above)

Remaining prostate will be submitted as follows:

Each slice/level is quadriseected into 1) left anterior 2) left posterior 3) right anterior and 4) right posterior, as with the apex and base margins. However, DO NOT cut the slices/levels into strips; submit as intact quadrant pieces and designate in the summary of sections (e.g., left anterior slice A should be "LAA", and left posterior slice A should be "LPA" and so forth).

A pathologist, blinded to the imaging results, will independently review all slides. Cases will be reported according to standard pathologic procedures including the presence of tumor, Gleason score, extracapsular extension, and seminal vesicle invasion. In addition, using an anatomical map of the prostate, each individual tumor

focus will be outlined and annotated (location within the gland, tumor size, tumor stage, and Gleason score). Any other abnormal areas/findings within the specimen will also be annotated. Immunohistochemical assessment of PSMA expression and/or neuroendocrine features will be performed as specified in source documentation. A tabular list of all cancer lesions will be made for each patient based on size and/or stage of each tumor and listing Gleason score, stage, and location. This list will be used to review and correlate with imaging findings on IAB2M PET/CT and mpMRI.

#### 9.1.3.2 Timing of Assessment

Histopathologic specimen assessment will occur after Visit 4, radical prostatectomy. Please refer to the Calendar of Events (Section 10).

## 9.2 **Special Studies**

### 9.2.1 Antigenicity Testing (HAHA)

#### 9.2.1.1 Method of Assessment

5 mL of whole blood will be drawn by peripheral venipuncture in a yellow top STT tube (5 mL) for HAHA evaluation.

#### 9.2.1.2 Timing of Assessment

Blood draws for HAHA determinations will be obtained on Visit 2, prior to  $^{89}\text{Zr}$ -df-IAB2M infusion and at Visit 5 (refer to Section 10).

## 10. STUDY CALENDAR

**Table 3: Schedule of Assessments**

Protocol Assessments	Screeninga Visit 1	Infusion Visit 2	Imaging Visit 3	Prostatectomy Visit 4	HAHA Visit 5
	Day -28 to -1	Day 0	Day 2 - 4	Within 3-30 days after visit 3 (preferably 1 week after scan)	6 Weeks ±1 week after Visit 4
Informed consent	X				
Demographics	X				
Medical history	X	X			
Concomitant medicationsb	X	X	X		
Physical exam	X	Xc			
Karnofsky Performance	X				
Vital signsc	X	X	X		
Blood lab samplesd	X	X	X		
Radiographic studiese	X	Xe	Xe	Xe	
HAHA Blood		Xf			Xf
Zr-df-IAB2M tracer administration		X			
Ga-PSMA-HBED-CC administration and PET/CT scan		Xg			
Zr-df-IAB2M PET/CT scan			X		
Adverse events		X	X		

a Screening evaluation should be performed following informed consent and within 4 weeks before enrollment, except when noted otherwise. Evaluations performed as standard of care before informed consent but within the 4-week window need not be repeated.

b Concomitant medication refers to medication received by subjects from the point of signed informed consent through the end of Visit 6.

c Vital signs include height, weight, temperature, blood pressure and heart rate. Height and weight are obtained only at Visit 1. During the Infusion Visit 2, serial vital signs will be monitored pre-infusion, then 30 minutes

and 60 minutes post-infusion ( $\pm 5$  minutes).

- d Laboratory samples collected include Chemistry panel, CBC (hematology), PSA (first blood draw only), and serum testosterone level (first blood draw only). All Screening laboratory samples are to be collected within 14 days before enrollment or at Visit 2, Pre-infusion (serum testosterone level may be up to 4 weeks before enrollment or Visit 2, prior to Zr-df-IAB2M infusion) and again at Visit 3.
- e Radiographic evaluations include a modified (3T multiparametric) MRI of the pelvis, if clinically indicated. Radiographic studies are to be performed within 6 weeks before, or on Visit 3/Day 2, provided the patient has not received a new intervening anti-cancer treatment.
- f Blood sample will be drawn via venipuncture for HAHA evaluation pre-infusion at Visit 3 and repeat samples will be taken at Visit 5 (week 6, +/- 1 week).
- g Ga-PSMA-HBED-CC administration followed by PET/CT scan 1 – 3 hours later must be done prior to Zr-df-IAB2M tracer administration on Visit 2 otherwise the Ga-PSMA-HBED-CC administration and PET/CT scan can be done anytime between screening and prostatectomy visit.

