### 1.2. Secondary Objectives

- To determine the correlation of  $^{89}\text{Zr}$ -df-IAB2M PET/CT findings with pathological features (i.e. Gleason pattern, diameter and PSMA-positivity).
- To compare the *in vivo*  $^{89}\text{Zr}$ -df-IAB2M PET/CT and  $^{68}\text{Ga}$ -PSMA-HBED-CC PET/CT to mpMRI.
- To determine the sensitivity, specificity, positive predictive value (PPV), negative predictive value (NPV) of IAB2M to detect all pathologically identified PCa lesions that do not meet criteria for clinical significance (defined as:  $< 0.5 \text{ cm}^3$  with Gleason pattern  $< 4$ ).
- Determine the proportion of IAB2M positivity (as measured by SUV) versus lesion size, Gleason pattern, and PSA levels.
- Determine ability of  $^{89}\text{Zr}$ -df-IAB2M PET/CT to identify extra-prostatic extension.
- Determine ability of  $^{89}\text{Zr}$ -df-IAB2M PET/CT to identify lymph node or other extra-prostatic involvement.
- To determine the safety of  $^{89}\text{Zr}$ -df-IAB2M PET/CT and  $^{68}\text{Ga}$ -PSMA-HBED-CC PET/CT imaging.

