**Amendment v3(01/27/17):**

**7.2 Ga-PSMA-HBED-CC Potential Risks**

There are no known contraindications for Ga-PSMA-HBED-CC. Because of the potential for infusion or allergic reaction, the subject should be monitored for safety for one hour following the infusion.

Based on prior studies, the known side effects, risks, and hazards associated with the administration of Ga-PSMA-HBED-CC include: infusion reaction (fever, chills, rash, hypotension, and/or hypertension after injection) and transient hepatic enzyme elevations. In addition, allergic reactions including anaphylaxis are a possibility.

**Radiation Dosimetry:** Radiation dose estimates for Ga-PSMA-HBED-CC were provided by [name] of *Technische Universität München (TUM)*, Munich, Germany. Balb1-c mice were used to determine the biodistribution at 4 time points after administration. Tissues were dissected after sacrifice and the percent of the administered dose was determined per organ and per gram of organ weight. The data of the biodistribution were extrapolated from mouse to man using OLINDA/EXM 1.0 Dosimetry Software.

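### 68Ga-PSMA-HBED-CC may be given after Visit 3, but Table 3 schedules no adverse event check or chemistry draw after that visit

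*Combined protocol and SAP*

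**What the plan says.** **Objective.** The last secondary objective in section 1.2 begins "To determine the safety of" and names both tracers.

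**When 68Ga may be given.** The grid in Table 3 puts its only 68Ga tick at Visit 2. Footnote g requires 68Ga to precede 89Zr-df-IAB2M if both fall on Visit 2. Otherwise the 68Ga "administration and PET/CT scan can be done anytime between screening and prostatectomy visit". Section 9.1.3 says the same: "The subject will be scheduled for the injection and imaging between screening and prostatectomy", according to the patient's availability.

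**What is scheduled.** The Table 3 row "Adverse events" is ticked at Visits 2 and 3. The blood sample row is ticked at Visits 1, 2 and 3. Footnote d opens with "Laboratory samples collected include Chemistry panel, CBC (hematology", does not name hepatic enzymes, and ends the draws with "and again at Visit 3". Visit 4 has only a radiographic tick and Visit 5 only the HAHA sample.

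**68Ga risk and acute monitoring.** Section 7.2 lists infusion reactions and "transient hepatic enzyme elevations", mentions possible allergic reactions, and says that "the subject should be monitored for safety for one hour following the infusion". Section 5.3 adds vital signs before infusion and at 30 and 60 minutes, and keeps a patient who is reacting at 60 minutes until the reaction resolves.

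**The concern.** The 68Ga dosing window runs past the last scheduled safety assessment. An enzyme change is a laboratory finding. Sections 5.3 and 7.2 describe an hour of observation with vital signs and no blood draw, so they would not find one. For a patient dosed after Visit 3, a delayed mild event or an enzyme rise enters the data only if it comes to light some other way.

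At stake is the 68Ga safety statement. Section 12.1 plans it only by pointing to the risks section and sets no denominator. Patients with no scheduled assessment beyond the first hour could be counted as event-free alongside patients who were examined and sampled.

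**Working it through.** The plan gives no figure to reproduce here. The check is a reading of Table 3 plus calendar arithmetic.

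**Inputs (Table 3).**
- Visit 2 = Day 0.
- Visit 3 = Day 2 to 4.
- Visit 4 (prostatectomy) = Visit 3 + 3 to 30 days.
- Visit 5 = Visit 4 + 6 weeks ±1 week, that is, + 35 to 49 days.

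**Visit days.**
- Visit 4: earliest 2 + 3 = Day 5; latest 4 + 30 = Day 34.
- Visit 5: earliest 5 + 35 = Day 40; latest 34 + 49 = Day 83.

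**Scheduled assessments after each possible 68Ga date.**
- *Before Visit 2:* adverse events are checked at Visits 2 and 3. Chemistry is drawn at Visit 3, and possibly earlier, because footnote d lets the screening samples be taken within 14 days before enrollment or at Visit 2 before infusion.
- *At Visit 2 (the ticked option):* adverse events and chemistry follow at Visit 3, 2 to 4 days later.
- *After Visit 3:* adverse event ticks at Visits 4 and 5, 0 of 2; blood sample ticks, 0 of 2.

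**Length of the exposed window.** It is the Visit 3 to Visit 4 interval, 3 to 30 days, or about 7 days on the preferred timing of one week after the scan.

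**Which existing visits could serve.** For a dose at least one day after Visit 3:
- to Visit 4: from 0 days (dose on the day of surgery) to 30 − 1 = 29 days;
- to Visit 5: from 0 + 35 = 35 days to 29 + 49 = 78 days.

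Only Visit 4 is near enough for an early check. Visit 5 can pick up events by recall, but surgery lies in between.

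**Do other sections fill the gap?**
- 5.3 and 7.2: first hour only, no blood draw.
- 5.5: six to seven weeks of follow-up after surgery, with no adverse event or laboratory content stated.
- 7: names laboratory tests as a part of safety monitoring, without dates.
- 7.4 and 11.1: record what is found, but schedule nothing.
- 7.5: serious events only.

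None of these dates an adverse event check or a chemistry draw after a late 68Ga dose.

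**The case against.** The strongest reply is that the gap is conditional and much is already covered. The grid places 68Ga at Visit 2, where Visit 3 follows with both assessments. The reactions most to be expected from an infusion fall within the monitored hour, a patient still reacting is kept, and imaging at 1 to 3 hours after infusion can extend the contact. Section 7.5 requires serious events on the study to be reported to the IRB and FDA, with no visit limit. Section 7.4 logs all adverse events. Footnote b to Table 3 carries concomitant medication beyond its ticked visits, so an empty cell does not prove that nothing is collected. The study is an exploratory pilot, safety is one of seven secondary objectives, and the primary endpoint is untouched.

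Most of this stands, and it limits the point to delayed non-serious events and post-dose chemistry. It does not remove the point: two places expressly permit late dosing, the adverse event row has no footnote like footnote b, and no section supplies a blood draw.

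Three stronger readings are tempting but unsupported:
- *That late-dosed patients go unmonitored, or that events after Visit 3 are discarded.* Sections 5.3, 7.2, 7.4 and 7.5 say otherwise.
- *That doses well before Visit 2 are missed in the same way.* They are followed by scheduled adverse event checks and at least the Visit 3 chemistry. The documents give no time course for the enzyme rise, so how well those draws would catch it cannot be judged.
- *That all 20 patients are affected.* The documents state neither how many receive 68Ga nor when.

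**Conclusion.** The point holds in limited form. Followed as written, the calendar gives a patient dosed with 68Ga after Visit 3 no scheduled check for delayed non-serious adverse events and no post-dose chemistry, within a window of 3 to 30 days before surgery. Immediate and serious events are covered.

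The number of patients affected is unknown and may be zero. The conclusion assumes that the Table 3 ticks are the full schedule for these two rows and that late dosing, being permitted, may be used. The yield of a later chemistry draw is also unknown without a time course. Severity is minor; this is a cheap improvement to the safety data.

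**What to change.** 1. Tick the adverse event row at the existing Visits 4 and 5. Ask at Visit 4 before the operation; at Visit 5, record whether onset was before or after surgery.
2. When 68Ga is given after Visit 3, require one chemistry panel that includes hepatic enzymes, after the dose and before surgery. Combine it with a pre-operative draw where one is taken.
3. In section 12.1, report 68Ga safety with the number of patients actually assessed after the dose.

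The cost is a few calendar and footnote edits, at most one extra blood draw per late-dosed patient, and some surgery-related events that need attribution. No new visit is needed. If nobody is dosed late, item 2 costs nothing.

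An alternative to item 2 is to confine 68Ga to Visit 2 or earlier. That needs no extra draw but gives up the scheduling flexibility that section 9.1.3 allows.
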